##### **4.1.4.1 Prophylactic measures**

###### **4.1.4.1.1 Premedication**

Premedication is mandatory 30-120 minutes prior to the administration of BI 836826 to prevent/reduce severity of infusion-related reactions, unless a contraindication for premedication exists. The premedication for the first and the second administration of the first course should include

- Acetaminophen/paracetamol 1000 mg p.o. or a clinically comparable dose, or equivalent
- Antihistamine *p.o.* or *i.v.*, equivalent to diphenhydramine 50 mg *i.v.*
- Glucocorticoid *i.v.*, equivalent to prednisolone 100 mg

**Proprietary confidential information.**

**© 2016 Boehringer Ingelheim International GmbH or one or more of its affiliated companies. All rights reserved.**

This document may not - in full or in part - be passed on, reproduced, published or otherwise used without prior written permission.

If BI 836826 has been well tolerated without signs of infusion-related reactions during the second administration, glucocorticoid premedication may be reduced to 50% of the administered dose starting with the third administration, *i.e.* glucocorticoid i.v., equivalent to prednisolone 50 mg at third administration and glucocorticoid i.v., equivalent to prednisolone 25 mg at fourth administration.

If a second and third course of 4 administrations is initiated, the premedication dose has to be repeated with glucocorticoid i.v., equivalent to prednisolone 100 mg at the first and second administration of BI 836826. If the infusion is well tolerated, glucocorticoid i.v. can be reduced as described above.

#### 4.1.4.1.2 Monitoring for infusion-related reactions

Close monitoring of the patient during and after the infusion of BI 836826 is required for evaluation of infusion-related risks. The measures of monitoring include:

- Hospitalization of patients with access to intensive care
- Frequent measurements and documentation of blood pressure and heart rate ([see section 5.2.5.1](#))

During the treatment the patients are required to be hospitalized under close surveillance with access to intensive care for at least 48 hours during the first infusion of BI 836826 and at least 24 hours during the second infusion (both in course 1). Hospitalization is also required for at least 24 hours during the first infusion in course 2. If there is no relevant infusion-related adverse events, the decision to hospitalize the patient is left to the discretion of the investigator.

If the split first dose administration is employed patients are required to be hospitalized under close surveillance with access to intensive care for at least 72 hours for the 1st visit in course 1 and at least 24 hours during the second infusion in course 2. Hospitalization is required for at least 24 hours during the first infusion in course 2. In case of no relevant infusion-related adverse events, the decision to hospitalize the patient is left to the discretion of the investigator.

#### 4.1.4.1.3 Tumour lysis syndrome

All patients have to be monitored for clinical or laboratory evidence of tumour lysis syndrome ([see section 5.2.3.2](#)). To prevent tumour lysis syndrome, all patients should receive appropriate hydration and allopurinol according to local standards or available guidelines ([R10-4517](#)). In addition, close monitoring of laboratory parameters to allow for early diagnosis of a possible tumour lysis syndrome is recommended, for details please refer to [section 5.2.3.2](#). CTCAE classifies TLS in grade 3 (present), grade 4 (life threatening consequences; urgent intervention indicated) and grade 5 (death). Presence of TLS is not clearly defined by CTCAE ([R10-4848](#)). For this trial the Cairo-Bishop classification will be used to define presence of TLS, *i.e.* presence of clinical TLS ([R10-4517](#)).

Proprietary confidential information.

© 2016 Boehringer Ingelheim International GmbH or one or more of its affiliated companies. All rights reserved.

This document may not - in full or in part - be passed on, reproduced, published or otherwise used without prior written permission.

#### 4.1.4.2 Handling of infusion-related reactions

In case of an infusion-related reaction, appropriate measures depending on the type and severity of the reaction should be taken by the investigator according to best medical judgement and local guidelines. Supportive therapy including steroids may be used as clinically indicated. The time between start and end of infusion may not exceed 24 hours. In case management of an infusion-related reaction would require more than 24 hours between start and end of the infusion of BI 836826, the infusion has to be stopped at 24 hours and the residual solution has to be discarded. The actual dose which has been administered prior to reaching this time limit has to be documented.

Changes of the infusion rate and temporary interruptions of the infusion have to be recorded in the eCRF.

Infusion-related reactions CTCAE grade 3 and 4 are defined to be significant adverse events and have to be reported according to the rules defined for SAE-reporting ([see section 5.2.2.1](#)).

The following recommendations for the management of infusion-related reactions may be considered by the investigator as guidance:

- In the case of an infusion-related reaction CTCAE grade 1, the infusion rate of BI 836826 should be reduced, *e.g.* to 50% of the target rate, or the infusion should be temporarily interrupted and resumed as soon as considered clinically manageable by the investigator.
- In the case of an infusion-related reaction CTCAE grade 2 or 3, the infusion with BI 836826 should be stopped immediately. Only in case all symptoms have resolved, administration of BI 836826 may be resumed. The investigator may consider to re-start at a slower infusion rate, *e.g.* of 50% of the target rate, and increase the infusion rate as tolerated to the target rate.
- In the case of an infusion-related reaction CTCAE grade 4, the infusion has to be stopped immediately. These patients should not be re-exposed to BI 836826 after the event.

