## 4. TREATMENTS

### 4.1 TREATMENTS TO BE ADMINISTERED

BI 836826 will be administered as an intravenous infusion. The first course of treatment has a duration of 7 weeks which starts with one infusion weekly 4 times followed by 27 days of observation after the 4th infusion ([Figure 3.1:1](#)), unless the split first dose administration described below will be implemented. A second course similar to course 1 can be administered, if the drug is well tolerated and the patient has no clinical signs of progression, judged by the treating physician. An additional third course of 4 weekly administrations can be given to the patients with response (*i.e.* complete or partial remission) and patients with stable disease, who tolerate the drug well and have clinical benefit. Clinical benefit can be improvement of clinical symptoms, and/or reduction in tumour size not meeting the criteria for a partial remission at the response assessment at the end of the second course.

The first infusion in each course should be started at a rate of 10 mL/h. The infusion rate can be increased every 30 (+/-10) minutes by 10 mL/h to a maximum of 80 mL/h as long as tolerated by the patient. If considered safe by the investigator, the subsequent infusions may be given with shorter interval for increasing the rate, but the maximum rate should not exceed 120 mL/h.

If adverse events which are considered related to the infusion schedule, *e.g.* infusion-related reaction, are not well controlled by the above schedule an alternative administration will be used. The first administration in course 1 will be split into two infusions, a low dose on day 1 followed by the full dose on the day 2. The first part of the administration will be 10% of the full dose, but not exceeding 10 mg given on day 1. The day after the second part of the administration will be the full planned dose for the patient (please refer the flowchart in [section 10.7](#)). The same infusion schedule should be employed as described above, starting with a rate of 10 mL/h. Premedication is mandatory before both infusions as they will be considered as the first administration ([section 4.1.4.1.1](#)). The potential change of the first infusion into two infusions will be assessed and may be modified by the DSMB. In subsequent administrations, the full dose of BI 836826 will be administered as a rate-controlled intravenous infusion on day 1.

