If symptoms of an infusion related reaction occur, the infusion should be temporarily stopped. Upon recovery, it should be resumed at 50% of the rate at which the reaction occurred for at least 30 minutes. Lower rates may be selected if clinically indicated. Depending on the time of occurrence and the severity of the reaction, the investigator may consider administering additional supportive medication, *e.g.* corticosteroids. A stepwise re-increase of the infusion rate to a maximum of 80 mL/h is possible.

For medical reason, the duration of the infusion may be expanded until the use-by date and use-by time indicated on the label is reached. The actual duration of the infusion needs to be documented in the eCRF including actual start and end time, actual time points for interruption and restart of the infusion and the actual infusion rates.

Proprietary confidential information.

© 2016 Boehringer Ingelheim International GmbH or one or more of its affiliated companies. All rights reserved.

This document may not - in full or in part - be passed on, reproduced, published or otherwise used without prior written permission.

Adverse events during the infusion should be thoroughly documented and characterized to allow differentiation between infusion-related reactions and tumour lysis syndrome ([R10-4428](#), [R10-4517](#)).

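### Protocol 4.1 and 4.1.4.2 conflict on grade 4 infusion reactions and differ in basis at grades 1 to 3; the split-dose hospital-stay text in 4.1.4.1.2 does not match other sections

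*Protocol*

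**What the plan says.** **Reaction handling.** Protocol 4.1 states: "If symptoms of an infusion related reaction occur, the infusion should be temporarily stopped". On recovery, "it should be resumed at 50% of the rate at which the reaction occurred for at least 30 minutes"; lower rates are allowed if clinically indicated. Then: "A stepwise re-increase of the infusion rate to a maximum of 80 mL/h is possible". No CTCAE grade is mentioned and there is no pointer to 4.1.4.2.

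Protocol 4.1.4.2 sets out recommendations by grade, introduced as ones that "may be considered by the investigator as guidance".
- Grade 1: reduce the rate, for example to half of a target rate, "or the infusion should be temporarily interrupted and resumed as soon as considered clinically manageable by the investigator".
- Grades 2 and 3: stop at once. Resumption is possible only after all symptoms have resolved. The investigator may consider a slower restart, with the example "of 50% of the target rate, and increase the infusion rate as tolerated to the target rate".
- Grade 4: stop, and do not expose the patient to the drug again.

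Protocol 5.2.2.1 lists infusion-related reactions of grade 3 or higher as protocol-specified significant events. If such an event is drug-related, it requires drug administration to be managed according to section 4.1.4.

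**Hospital stay.** Protocol 4.1.4.1.2 has two paragraphs. The standard-dose paragraph asks for at least 24 hours in hospital at the second infusion of course 1. The split-dose paragraph asks for 72 hours at the first visit of course 1, then 24 hours at the second infusion of course 2 and 24 hours at the first infusion of course 2. Both paragraphs leave hospitalization to the investigator if there are no relevant infusion-related events.

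**The concern.** Two sections of one protocol tell sites what to do in the same acute event, and neither refers to the other on these rules. A site that opens 4.1 finds an instruction to resume with no upper limit on grade. A site that opens 4.1.4.2 finds that a grade 4 patient should not receive the drug again. At lower grades the sections tie the restart rate to different quantities, and one of those quantities is undefined.

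The split-dose paragraph applies when infusion-related events have not been well controlled on the standard schedule (Protocol 4.1). It names a different second infusion from the one named in the standard-dose paragraph above it. What is at stake is consistent handling of reactions across sites, not the trial's error rates or size.

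**Working it through.** No figure in the plan needs reproducing, so the check sets the sections side by side.

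**Step 1: reaction handling by grade**

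| Grade | Protocol 4.1 | Protocol 4.1.4.2 | Can a site satisfy both? |
|---|---|---|---|
| 1 | Stop, resume at half the running rate or lower | Slow down, or interrupt and resume when manageable | Yes, by following 4.1. Slowing without stopping does not meet 4.1 |
| 2 and 3 | As above | Stop; resume only after all symptoms resolve; slower restart optional | Yes, by following 4.1 and waiting for full resolution. Restarting at the previous rate is not ruled out by 4.1.4.2 but does not meet 4.1 |
| 4 | As above, no exception written | Stop, no re-exposure | No, unless 4.1.4.2 is read as overriding 4.1, which is not written |

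**Step 2: basis of the restart rate.** Let R be the rate at which the reaction occurred and T the target rate.
- Section 4.1: restart at 0.5 × R.
- Section 4.1.4.2 (example only): restart at 0.5 × T.
- The two are equal only if T = R.

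Section 4.1 supplies a starting rate of 10 mL/h and a step rule: "The infusion rate can be increased every 30 (+/-10) minutes by 10 mL/h to a maximum of 80 mL/h". For later infusions it adds that "the subsequent infusions may be given with shorter interval for increasing the rate, but the maximum rate should not exceed 120 mL/h". These are a start, a step and two ceilings; none is called a target. T therefore has no value in the visible text, and 0.5 × T cannot be calculated. For the same reason, one cannot tell whether increasing to T respects the 80 mL/h ceiling that 4.1 sets after a reaction.

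**Step 3: standing of the list.** Section 4.1.4.2 calls its list guidance. Section 5.2.2.1 makes management according to 4.1.4 mandatory for drug-related reactions of grade 3 or higher. Section 4.1.4 contains that list and also the continuation criteria of 4.1.4.4. The reaction paragraph of 4.1 lies outside 4.1.4. The text does not say whether the mandatory reference turns the list into a rule.

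**Step 4: which second infusion.** Protocol 4.1 counts both split infusions (days 1 and 2) as the first administration, so the second administration of course 1 falls on day 8.

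| Section | Second administration or infusion, course 1 | Second infusion, course 2 |
|---|---|---|
| 4.1.4.1.2, standard dose | 24 h in hospital | Not named |
| 4.1.4.1.2, split dose | Not named | 24 h in hospital |
| 5.2.3.2 (tumour lysis) | Monitoring for 24 h; under split dosing, other infusions as for standard dosing | Monitoring while in hospital |
| 5.2.5.1 (vital signs) | Monitoring for at least 24 h | Not named for 24 h; the 24 h period is at the first infusion of course 2 |
| 6.1 | Surveillance may be shortened, up to 24 h | Out-patient possible if the first infusion of course 2 was well tolerated |
| 6.2.2.1 | First two administrations in hospital | Only the first administration of course 2 is described as in hospital (6.2.2.2) |

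There are thus two mismatches. The split-dose paragraph is silent on day 8, where the other sections are not. On the second infusion of course 2, the split-dose paragraph and 5.2.3.2 point to hospital, while 6.1 allows an out-patient visit.

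**The case against.** The strongest reply is that a careful reader can reconcile most of this. The 4.1.4.2 list is advisory, its 50% is an example, and it asks for a reduced or slower rate. Section 4.1 is the more specific on rate and permits lower rates. At grade 4 the graded text can be taken as the specific rule that displaces the general one. The reference in 5.2.2.1 is to 4.1.4 as a whole, which can be followed while one list in it stays advisory. All of that stands for grades 1 to 3. At grade 4 it leaves the reader to supply a priority rule that the protocol does not state, in the most severe non-fatal case.

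Three stronger readings are tempting, and the documents do not support them.
- **A quantified gap in mL/h.** A reader might take the target rate to be 80 or 120 mL/h and compute large differences. No section says so, and at low running rates such a restart would be faster than the rate that provoked the reaction, against the wording of 4.1.4.2 itself.
- **An effect on the primary analysis.** A patient who is not re-exposed before completing two administrations is replaced (Protocol 3.3.4.1) and excluded from the primary endpoint analysis (SAP 7.4). A reader might infer bias in the MTD. That needs a grade 4 reaction that early, a site that resumes despite 4.1.4.2, and a patient who then meets the continuation criteria of 4.1.4.4. Replacement restores the cohort, and Protocol 5.2.1.1 excludes infusion-related reactions from DLT.
- **No supervision on day 8 under split dosing.** Sections 5.2.3.2, 5.2.5.1, 6.1 and 6.2.2.1 still cover it.

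**Conclusion.** The point holds, at minor severity. Protocol 4.1 and 4.1.4.2 contradict each other as written for grade 4 reactions. At grades 1 to 3 they differ in the basis and strength of the instruction, without an unavoidable conflict. The term target rate is undefined in the visible text, and the standing of the 4.1.4.2 list is unclear against 5.2.2.1. The split-dose paragraph of 4.1.4.1.2 does not match the other sections for the second administration of course 1, and the documents also disagree among themselves on the second infusion of course 2.

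The size is qualitative: no DLT definition, sample size or analysis rule is affected, and no rate difference can be calculated. This rests on the visible text. A definition of target rate in the investigator site file or in removed text could not be checked and would settle that one element.

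**What to change.** The passages must be reconciled; which clinical rule applies is for the sponsor to decide.
- Align 4.1 and 4.1.4.2 on grade 4 handling, on the basis for the restart rate, on whether a slower restart is required or optional, and on grade 1 handling. Add a cross-reference in each.
- Define the target rate or remove the term.
- State whether the 4.1.4.2 list is guidance or binding, consistently with 5.2.2.1.
- Align the split-dose paragraph of 4.1.4.1.2 with 5.2.3.2, 5.2.5.1, 6.1 and 6.2.2.1 for the second infusions of courses 1 and 2.

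The cost is wording in a protocol amendment or a site clarification letter. No SAP change and no new analysis is needed.

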#### 4.1.4.3 Management of infections:

During treatment with BI 836826 patients need to be carefully monitored for infections at each clinic visit. Frequent blood counts monitoring will help to identify patients with prolonged neutropenia who might be at risk for severe infections. It is highly recommended that the treatment of infection starts immediately upon very first clinical symptoms. Depending on investigators' assessment the use of growth factors, antibiotics, antifungals, and antivirals should be considered, and implemented with no delay. The next administration of BI 836826 needs to be delayed until the patient has cleared an infection and has recovered from neutropenia as outlined in sec: 4.1.4.4

#### 4.1.4.4 Continuation of Treatment during a Course, or beginning a new course

Adverse events and laboratory values will be evaluated continuously by the sponsor. Prior to each administration of BI 836826, adverse events and safety laboratory will be assessed. To

**Proprietary confidential information.**

**© 2016 Boehringer Ingelheim International GmbH or one or more of its affiliated companies. All rights reserved.**

This document may not - in full or in part - be passed on, reproduced, published or otherwise used without prior written permission.

continue treatment with a further infusion of BI 836826, all of the following criteria must be met:

- (1) No active infection
- (2) Neutrophils  $\geq 1000 / \mu\text{L}$  ( $1.0 \times 10^9 / \text{L}$ ) and platelets  $\geq 25.000 / \mu\text{L}$  ( $25 \times 10^9 / \text{L}$ ), with or without growth factor support or transfusions.
- (3) no evidence of progressive disease
- (4) Acceptable tolerability (in case of an adverse event at the planned start of a treatment course, patients may continue therapy only after recovery to a level which would allow further therapy, *i.e.* CTCAE grade 1 or pre-treatment value.)

In case criterion 1 and/or 4 is not fulfilled, blood counts and/or the adverse event should be re-evaluated for up to three weeks. A delay during a course should be communicated to the clinical monitor at Boehringer Ingelheim. As soon as all criteria 1-4 are met, the investigator in agreement with the clinical monitor at Boehringer Ingelheim may continue the treatment (unless other criteria for discontinuation or withdrawal apply, see [section 3.3.4.1](#)). If a visit with administration of BI 836826 is delayed, all subsequent visits with treatment administration will be recalculated based on the actual date of delayed visit. If a visit is delayed less than 5 days, the delay may be caught up by shortening the observation period of the course after agreement between investigator and clinical monitor of the trial, provided that patient fulfills all the requirement for the next treatment ([see section 6.1](#)).

In case an adverse event is continuing at a CTCAE grade 2 or higher without recovery to grade 1 within 5 weeks after the last BI 836826 infusion and this is above the pre-treatment level, the investigator in agreement with the clinical monitor at Boehringer Ingelheim may continue BI 836826 only in the case that the event is considered not drug-related by investigator and sponsor.

Administration of the trial drug has to be stopped temporarily in case of a DLT (see [section 5.2.1.1](#)). Patients may continue therapy only after recovery from the DLT to at least CTCAE grade 1 or pre-treatment value. The future dose of BI 836826 must be finally agreed on between the sponsor and the investigator. A reduction of the dose will be allowed only once for an individual patient during the whole trial. Treatment has to be discontinued in case the DLT is not reversible.

Intra-patient dose-escalation of BI 836826 will not be allowed in this trial.

During the dose-escalation phase, the first course (4 administrations as weekly infusions) should be given to all patients. In absence of clinical progression judged by the investigator, treatment with BI 836826 can be continued for the second course, (*i.e.* another 4 administrations) in agreement with the investigator and the clinical monitor of the sponsor. Patients with a complete or partial remission by CT scan after 8 administrations or stable disease with improvement in clinical symptoms may receive additional 4 administrations weekly as consolidation therapy after discussion between the investigator and the clinical

**Proprietary confidential information.**

**© 2016 Boehringer Ingelheim International GmbH or one or more of its affiliated companies. All rights reserved.**

This document may not - in full or in part - be passed on, reproduced, published or otherwise used without prior written permission.

monitor of the sponsor. Continuation of BI 836826 beyond 12 administrations will only be possible on a case by case basis after discussion between the investigator and the clinical monitor of the sponsor.

A log of all patients enrolled into the study (*i.e.* having given informed consent) will be maintained in the ISF at the investigational site irrespective of whether they have been treated with investigational drug or not.

